6. STUDY POPULATION

6.1. Inclusion Criteria

Patients meeting all of the following criteria must be enrolled in the study:

1. All patients must have histologically or cytologically confirmed, advanced, relapsed or metastatic gastric or gastroesophageal junction adenocarcinoma.
2. Patient is ≥ 18 years of age (or country's legal age of majority if the legal age was > 18 years) at the time of obtaining informed consent.
3. Patient must have one of the following diagnoses to be eligible for enrollment into cohorts:
 - A. Cohort 1: Checkpoint inhibitor naïve Epstein-Barr Virus negative (EBV-) gastric cancer patient who has had a disease progression after at least 2 prior systemic treatments for advanced or metastatic gastric cancer
 - B. Cohort 2: Checkpoint inhibitor naïve Epstein-Barr virus positive (EBV+) gastric cancer patient (as determined by standard methods, e.g. EBER ISH or LMP-1 IHC) who had at least 1 prior systemic treatment for advanced or metastatic gastric cancer
4. Patient has an Eastern Cooperative Oncology Group (ECOG) performance status of 0 or 1 and has a life-expectancy ≥ 3 months.
5. Patient's interval from prior to the first study dose is at least 4 weeks for systemic anticancer therapy including investigational agents (or at least 5 half-lives for investigational/ non-cytotoxic agents, whichever is longer. Upon discussion with the Medical Monitor, fewer than stated wash-out period may be allowed provided that the patient has adequately recovered from any clinically relevant toxicity).
6. Patient must have at least one measurable lesion at baseline by computed tomography(CT) or magnetic resonance imaging (MRI) per Response Evaluation Criteria in Solid Tumors (RECIST v1.1) Lesions situated in a previously irradiated area are considered measurable if progression has been demonstrated in such lesions.
7. Demonstrate adequate organ function as defined in Table 1.1:1. All screening labs should be performed within 14 calendar days prior to the first study dose.

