9.1.2. Timing of Tumor Imaging

9.1.2.1. Screening

Initial tumor imaging at Screening must be performed within 30 days prior to Cycle 1, Day 1. The investigator must review screening images to confirm that the subject has measurable disease per RECIST 1.1. Historical CT or MRI scans performed within 30 days before the start of study treatment, may be used as screening scans, provided they meet minimum standards. The image will be sent to central imaging for further analysis.

Confirmation of measurable disease based on RECIST 1.1 using local assessment at Screening will be used to determine subject eligibility.

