9.1.2.2. During Treatment

All images during treatment will be sent to central imaging for further analysis. The first imaging assessment during study treatment should be performed 6 weeks (± 7 days) from Cycle 1, Day 1.

Subsequent tumor imaging should be performed every 6 weeks (± 7 days) or more frequently if clinically indicated for the first year of treatment. After 1 year, subjects who continue to receive study treatment will have imaging performed every 9 weeks (± 7 days) for up to 1 additional year.

The timing of tumor imaging should follow calendar days and should not be adjusted for delays in cycle starts. Tumor imaging should continue to be performed until Progressive Disease (PD) is identified by the investigator (unless the investigator elects to continue treatment and follow iRECIST), the start of new anticancer therapy, withdrawal of consent, loss to follow-up, death, 2 years of study treatment, or termination of the study by the Sponsor, whichever occurs first.

Objective response should be confirmed by a repeat imaging assessment. Tumor imaging to confirm PR or CR should be performed at least 4 weeks after the first indication of a response is observed. Subjects will then return to regularly scheduled imaging, starting with the next scheduled imaging time point. Subjects who receive additional imaging for confirmation do not need to undergo the next scheduled tumor imaging if it is less than 4 weeks later; tumor imaging may resume at the subsequent scheduled imaging time point.

Per iRECIST, investigator-assessed Progressive Disease (PD) in the clinically stable subjects should be confirmed by the investigator 4 to 8 weeks after the first radiologic evidence of Progressive Disease (PD). A subject with unconfirmed Progressive Disease may continue to receive study treatment at the discretion of the investigator until progression is confirmed by the investigator, provided the subject has met the conditions detailed in Section 9.1.3. Subjects who have confirmatory imaging do not need to undergo the next scheduled tumor imaging assessment if it is less than 4 weeks later; tumor imaging may resume at the subsequent scheduled imaging time point, if clinically stable.

Subjects who have confirmed Progressive Disease (PD) by iRECIST, as assessed by the investigator, will discontinue study treatment. Exceptions are detailed in Section 9.1.3.

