PFS is defined as the time from the date of first administration of study treatment to determination of tumor progression by RECIST version 1.1 or death due to any cause, whichever occurs first.

According to iRECIST, Best Overall Response (iBOR) of complete response (CR/iCR), partial response (PR/iPR), stable disease (SD/iSD), Progressive disease (iPD) or unevaluable (iUE) will be derived. iORR, iDCR, iTTR, iDoR and iPFS will be analyzed in the same manner as used analyses in accordance with RECIST 1.1.

iPD is defined as the time point of first iUPD without subsequent iSD, iPR or iCR before study treatment discontinuation.

OS is defined as the duration of time from the treatment start date to time to death from any cause. If subjects survive at the time of analysis, the subject will be censored at the last date of survival confirmed.

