### 12.2 Time to Event Endpoints (TTR, DoR, PFS and OS)

The time to event endpoints, including time to response (TTR), duration of response (DoR), progression-free survival (PFS) and overall survival (OS) will be summarized descriptively and graphically by the Kaplan-Meier methodology, as described in Section 3.3.

TTR is defined as the time from the date of first administration of study treatment to first documented CR or PR. DoR is measured from the date of the first observation of tumor response (CR or PR, whichever occurs first) to the date of disease progression or death for the subject with an objective response. PFS is defined as the time from the date of first administration of study treatment to determination of tumor progression by RECIST version 1.1 or death due to any cause, whichever occurs first. OS is defined as the duration of time from the treatment start date to time to death from any cause. If subjects survive at the time of analysis, the subject will be censored at the last date of survival confirmed.

TTR, DoR, PFS, and OS will be calculated in days, as well as in months.

For the tumor-related time-to-event endpoints, subjects who have not experience any event (Progressive Disease (PD) or Death) at the time of analysis will be censored at the date of the last evaluable tumor assessment. However, if the subject progresses or dies after two or more consecutive missed assessments

or start of new anticancer therapy, the subject will be censored at the time of the last evaluable assessment prior to starting new anti-cancer therapy/missed assessments. If the subject has no evaluable baseline/post-baseline assessment, subject will be censored at the date of first administration of study treatment. In case of subjects entering the extension part, the data will be treated as censored at the date of the last evaluable tumor assessment on or before the first administration date in the extension part.

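### The rule that censors PFS at first dose states no exception for death, so a death before the week-6 scan can be read as censored on Day 1

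*SAP*

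**What the plan says.** Protocol 11.4.2 runs PFS from first administration "to determination of tumor progression by RECIST version 1.1 or death due to any cause, whichever occurs first", and SAP 12.2 defines it the same way. Three censoring sentences for the tumor-related time-to-event endpoints then follow in both documents.

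1. The first covers "subjects who have not experience any event (Progressive Disease (PD) or Death) at the time of analysis" and censors them at the last evaluable tumor assessment.
2. The second overrides an event: "if the subject progresses or dies after two or more consecutive missed assessments", or does so after starting new anticancer therapy, the subject is censored at the last evaluable assessment before that point.
3. The third reads: "If the subject has no evaluable baseline/post-baseline assessment, subject will be censored at the date of first administration of study treatment".

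SAP 12.2 adds a rule for subjects entering the extension part, which does not bear on this point. SAP 12.1 has iPFS analysed in the same manner as PFS. SAP 3.3 summarises time-to-event endpoints by Kaplan-Meier quartiles with 95% confidence intervals. SAP 2.4 plans no formal testing.

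**The concern.** The third sentence carries neither an event-free condition nor an exception for death. Two things are left open: whether the slash means that either assessment is missing or that both are, and whether the sentence stands alone or only completes the first.

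The subject affected is one who is treated and dies before the first on-treatment scan. If the rule is programmed as written, with the slash as 'either', that death becomes a censored observation at time zero. The risk set then loses a subject who had a PFS event, and the Treated Set curves for PFS and iPFS move upward. Another programmer could follow the same text and count the death.

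**Working it through.** **Which rule reaches an early death.** Take a subject who dies in week 3.

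- Baseline: entry criteria state "Patient must have at least one measurable lesion at baseline" (Protocol 6.1), and Protocol 9.1.2.1 adds "The investigator must review screening images to confirm that the subject has measurable disease per RECIST 1.1". The subject therefore has a baseline assessment.
- Post-baseline: "The first imaging assessment during study treatment should be performed 6 weeks" from Cycle 1 Day 1, within 7 days either side (Protocol 9.1.2.2). The subject has no post-baseline assessment and has missed none.
- Sentence 1 does not apply, because the subject has an event. Sentence 2 does not apply, because no assessment was missed and no new therapy started. Only the PFS definition and sentence 3 remain, and taken literally they conflict.

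**The slash.** Since entry requires a baseline scan, 'both missing' would leave the sentence with almost nothing to do. 'Either missing' is therefore likelier, but that is an inference.

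**Size on the literal reading.** The plan gives no PFS figure to reproduce. Let N be the number treated and d the deaths before any post-baseline scan. Assume no other subject is censored at Day 1 or before the last of these deaths, and let S_rest be the curve for the other N-d subjects. After the last early death:

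- deaths counted: S(t) = [(N-d)/N] x S_rest(t)
- deaths censored at Day 1: S(t) = S_rest(t)
- ratio: N/(N-d) = 1/(1-d/N)

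This gives 1/0.95 = 1.05, 1/0.90 = 1.11 and 1/0.80 = 1.25 for early-death shares of 5%, 10% and 20%. If c others are also censored at Day 1, the ratio is (N-c)/(N-c-d); with N = 30, c = 3, d = 3 it is 27/24 = 1.125. Censoring at Day 1 gives the same curve as leaving the subject out.

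**Effect on the planned quartiles.** The literal curve reaches 50% where the curve with deaths counted stands at 0.50 x (1-d/N): 0.475, 0.45 and 0.40 for the three shares. The other quartiles shift in the same way.

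An illustration uses the cohort maxima in SAP 3.7 (60 and 30). Assumptions: target median m = 3 months; week 6 = 42/30.4375 = 1.38 months; exponential events after week 6 with rate ln[(1-d/N)/0.5]/(m-1.38), placed at evenly spaced quantiles; no other censoring.

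| N | d | Median, deaths counted (months) | Median, literal (months) |
|---|---|---|---|
| 60 | 3 (5%) | 2.96 | 3.13 |
| 60 | 6 (10%) | 2.95 | 3.24 |
| 60 | 12 (20%) | 2.94 | 3.70 |
| 30 | 3 (10%) | 2.91 | 3.29 |
| 30 | 6 (20%) | 2.89 | 3.63 |

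**Against sampling error.** Take N = 30, d = 3 and an assumed 12-week median for the rest. Then S_rest(18 weeks) = 0.5^(18/12) = 0.354, and with deaths counted the value is 0.354 x 27/30 = 0.318. The shift is 3.5 points against a binomial standard error of sqrt(0.318 x 0.682/30) = 8.5 points, or 0.42 standard errors. Week-18 PFS is not a planned summary, and this one case is not a bound.

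**The case against.** The strongest reply is that sentence 3 is only a fallback date. Sentence 2, which does override an event, names progression and death; sentence 3 names neither. Sentences 1 and 2 both censor at a last evaluable assessment, and sentence 3 supplies the date when there is none. The definition of PFS a few lines earlier counts every death. On this reading the paragraph is coherent and an early death stays an event.

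That argument stands as a good reading, but it does not close the question. A subject who misses the week-6 and week-12 scans and then dies is censored by sentence 2 and has no post-baseline assessment, so sentence 3 is also needed for some subjects who have died. Its scope cannot simply be assumed to be event-free subjects.

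The consequences are limited. Eligibility asks for ECOG "performance status of 0 or 1 and has a life-expectancy" of at least 3 months, which should keep such deaths few without ruling them out. The Tumor Evaluable Set would not expose the difference, since it requires a completed cycle and evaluability for response. OS does count every death, however, and those recorded as adverse events appear in the outputs for TEAEs leading to death.

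A reader might infer that the SAP definitely censors early deaths, or that they would be hidden from every output. The documents support neither. SAP 12.3 and the table, listing and figure lists show no readable content and count neither way.

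**Conclusion.** The sentence is ambiguous. Applied as written, with the slash read as 'either', it censors a PFS event at Day 1; the fallback reading is equally open and would give the correct result. On the literal reading, later PFS and iPFS values are inflated by N/(N-d), about 5% to 25% in relative terms for early-death shares of 5% to 20%, and the quartiles move up. Those shares are assumptions, and the factor requires no other censoring at Day 1 or before the last early death. The median shifts rest further on the assumed 3-month target and exponential shape.

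A reader might take this to threaten the trial's decisions. It does not: ORR, the go/no-go rule and OS do not use this sentence, and PFS and iPFS are secondary and descriptive. Severity is minor.

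**What to change.** In SAP 12.2, keep the existing sentence for the other tumor-related endpoints and add:

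> For PFS and iPFS, censoring at first administration for lack of an evaluable baseline or post-baseline assessment applies only to subjects without a PFS (or iPFS) event. A death before the first post-baseline assessment is an event on the date of death, unless it falls under the existing rule on consecutive missed assessments or new anticancer therapy; in that case, with no evaluable post-baseline assessment, the subject is censored at first administration.

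This settles the slash, leaves TTR with its rule, and keeps a documented progression as an event on its own date even when the baseline is not evaluable. Protocol 11.4 leaves technical detail to the SAP, so Protocol 11.4.2 can be aligned at the next amendment.

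No new data are needed. If the fallback reading was always intended, no result changes. Otherwise PFS may become slightly less favourable.

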### 12.3 Sensitivity Analysis

### 13. SAFETY

Safety endpoints will be analyzed using the treated set. Safety endpoints will be summarized descriptively as described in section 3.1.

#### 13.1 Adverse Events

All AEs including will be coded using the most recent version of the MedDRA coding dictionary, graded using NCI-CTCAE version 5.0.

Treatment emergent adverse events (TEAEs) are defined as adverse events occurring from the first dose of the study treatment through 30 days following cessation of study treatment will be considered 'treatment-emergent'. Adverse events that start before first study treatment and deteriorate under treatment will also be considered as 'treatment-emergent'.

All AE summaries will be restricted to TEAEs only and all the study drug related AE will be summarized [REDACTED]. Summary tables will include the number of participants (%) experiencing an event and the number of events. Subjects will be counted only once for each SOC and PT level (categorical descriptive analysis). For each TEAE, the most extreme grade recorded in eCRF will be attributed and used in the by-severity summaries.

The TEAE summaries will include:

- Overall summary of TEAEs
- Summary of TEAEs by SOC and PT
- Summary of TEAEs by SOC, PT and Severity
- Summary of SAEs by SOC and PT
- Summary of SAEs by SOC, PT and Severity
- Summary of ECIs by SOC and PT
- Summary of ECIs by SOC, PT and Severity
- Summary of TEAEs Related to (any study drug [REDACTED]) by SOC and PT
- Summary of TEAEs Related to (any study drug [REDACTED]) by SOC, PT and Severity
- Summary of SAEs related to (any study drug [REDACTED]) by SOC and PT
- Summary of TEAEs leading to (any study drug [REDACTED]) dose modification (reduction / interruption) by SOC and PT
- Summary of TEAEs leading to (any study drug [REDACTED]) discontinuation by SOC and PT
- Summary of TEAEs leading to death by SOC and PT

Separate by-subject data listings will be created for

- TEAEs
- SAEs
- TEAEs leading to dose modification (reduction/interruption)
- TEAEs leading to drug discontinuation
- TEAEs leading to death
- Adverse events reported prior to treatment but after informed consent

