7.3.2. Pembrolizumab

Adverse events associated with pembrolizumab exposure may represent an immunologic etiology. These immune-related AEs (irAEs) may occur shortly after the first dose or several months after the final dose of pembrolizumab. Therefore, early recognition and initiation of treatment is critical to reduce complications. Based on existing clinical study data, most irAEs are reversible and can be managed with interruptions of pembrolizumab, administration of corticosteroids, and/or other supportive care. Suspected irAEs should be adequately evaluated to confirm etiology or exclude other causes. Additional procedures or tests such as bronchoscopy, endoscopy, skin biopsy may be included as part of the evaluation. Based on the severity of irAEs, Pembrolizumab should be withheld or permanently discontinued, and corticosteroids administered. Pembrolizumab may cause severe or life-threatening infusion-reactions including severe hypersensitivity or anaphylaxis. Signs and symptoms usually develop during or shortly after drug infusion and generally resolve completely within 24 hours of completion of infusion.

Criteria for dose delay, modification, or discontinuation of pembrolizumab are described below, and are based on criteria in the Keytruda Investigator's Brochure.

Table 7.3:2 shows treatment guidelines, including premedications, for subjects who experience an infusion reaction associated with the administration of pembrolizumab.

Dose modification and toxicity management guidelines for irAEs associated with pembrolizumab are provided in Table 7.3:3 .

Pembrolizumab may be interrupted for situations other than treatment-related AEs, such as medical or surgical events and/or unforeseen circumstances not related to study intervention. However, pembrolizumab is to be restarted within 3 weeks of the originally scheduled dose or within 42 days of the previously administered dose, unless otherwise discussed with the Sponsor. The reason for interruption is to be documented in the subject's eCRF.

Table 7.3:2 Infusion Reaction Treatment Guidelines for Pembrolizumab

CTCAE(v5.0) Grade	Treatment	Premedication for Subsequent Doses of Pembrolizumab
Grade 1 Mild reaction; infusion interruption not indicated; intervention not indicated	Increase monitoring of vital signs as medically indicated until the participant is deemed medically stable in the opinion of the investigator.	None

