2. An elevated AST or ALT value that is ≥ 3 times the upper limit of normal (\times ULN) and an elevated total bilirubin value that is $\geq 2 \times$ ULN and, at the same time, an alkaline phosphatase value that is $< 2 \times$ ULN, as determined by protocol-specified laboratory testing or unscheduled laboratory testing.*

**Note: These criteria are based upon available regulatory guidance documents. The purpose of the criteria is to specify a threshold of abnormal hepatic tests that may require an additional evaluation for an underlying etiology. The study site guidance for assessment and follow up of these criteria can be made available. It may also be appropriate to conduct additional evaluation for an underlying etiology in the setting of abnormalities of liver blood tests including AST, ALT, bilirubin, and alkaline phosphatase that do not meet the criteria noted above. In these cases, the decision to proceed with additional evaluation will be made through consultation between the study investigators and the Sponsor or medical monitor. However, abnormalities of liver blood test values that do not meet the criteria noted above are not ECIs for this study.*

3. QTcF interval ≥ 450 ms or a > 60 ms increase from baseline (defined as average QTcF value from C1D1 pre-dose ECGs).
4. Significant GI toxicity, e.g., nausea, vomiting, diarrhea, or constipation not easily managed with symptomatic medications in an outpatient setting.

In addition to the above ECIs, Events Associated with Special Situations include pregnancy or exposure to study treatment through breastfeeding; AEs associated with study treatment overdose, or medication error. Events associated with special situations and ECIs are to be captured using the SAE procedures but are to be considered as SAEs only if they meet one of the above criteria. All ECIs and AEs associated with special situations are to be reported on a completed SAE form by email or fax whether or not they meet the criteria for SAEs, and are subject to the same reporting timelines described in Section **10.1.1**.

Serious adverse events must be reported after the consent form is signed through 90 days following cessation of study treatment, or 30 days after final dose if the subject initiates new anticancer therapy, whichever occurs first.

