All SAEs must be followed to resolution or, if resolution is unlikely, to stabilization. Any SAE judged by the investigator to be related to the study treatment or any protocol-required procedure should be reported to the Sponsor regardless of the length of time that has passed since study completion.

The following hospitalizations are not considered to be SAEs because there is no “adverse event” (i.e., there is no untoward medical occurrence) associated with the hospitalization:

- Hospitalizations for respite care
- Planned hospitalizations required by the protocol
- Hospitalization planned before informed consent (where the condition requiring the hospitalization has not changed after study treatment administration)

- Hospitalization for administration of study treatment or insertion of access for administration of study treatment
- Hospitalization for routine maintenance of a device (e.g., battery replacement) that was in place before study enrollment

If possible, blood sample(s) for the measurement of FLX475 and pembrolizumab plasma concentrations should be drawn at the first report of an SAE or a severe unexpected AE and at its resolution. See Section [10.1.1](#) for SAE reporting requirement.

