11.4.3. Safety Analysis

All adverse events will be coded using the most recent version of the Medical Dictionary for Regulatory Activities (MedDRA) coding dictionary, graded using NCI-CTCAE version 5.0 and listed by subject.

Statistical analysis and reporting of adverse events will concentrate on treatment-emergent adverse events (TEAEs). To this end, all adverse events occurring from the first dose of the study treatment through 30 days following cessation of study treatment will be considered 'treatment-emergent'. Adverse events that start before first study treatment and deteriorate under treatment will also be considered as 'treatment-emergent'.

Incidence of TEAEs will be summarized by maximum severity and causal relationship with either FLX475 or pembrolizumab using System Organ Class(SOC) and Preferred Term(PT) of MedDRA. Incidence of ECIs, SAEs, TEAEs leading to dose modification (reduction/interruption), drug discontinuation or death also be summarized respectively, and the list will be provided as appropriately.

Adverse events reported prior to treatment but after informed consent will be provided in a listing.

Laboratory test result will be summarized both quantitatively as well as qualitatively by planned time point. For the quantitative parameter, the actual value and the change from baseline will be summarized using System International (SI) units. Shift table, which display a cross-tabulation of the baseline grade versus the worst grade until ED/EOT will be provided for both of the NCI-CTCAE(v5.0) grade and investigator's clinical significance abnormality assessment.

Vital signs and 12-Lead ECG parameter will be summarized descriptive statistics for the actual value and the change from baseline. In addition, for 12-Lead ECG parameter, the shift table will be presented for the investigator's clinical significance abnormality assessment.

All clinically significant abnormality from the laboratory test, vital signs, and 12-Lead ECG will be classified according to NCI-CTCAE(v5.0) and also be reported as adverse events.

[REDACTED]

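### SAP 13.1 limits the SAE, related-SAE and fatal-event tables to TEAEs, so SAEs starting 31 to 90 days after treatment are collected but not tabulated

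*SAP*

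**What the plan says.** SAP 13.1 defines TEAEs as "adverse events occurring from the first dose of the study treatment through 30 days following cessation of study treatment", plus events that began before dosing and worsened on treatment. It then sets a general rule: "All AE summaries will be restricted to TEAEs only and all the study drug related AE will be summarized" (the end of this sentence is redacted). The list of TEAE summaries that follows includes "Summary of SAEs by SOC and PT", the same by severity, a table of SAEs related to study drug, and a table of TEAEs leading to death. Among the by-subject listings, the SAE listing carries no TEAE limit, but the death listing covers only TEAEs leading to death.

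The protocol collects SAEs for longer. Section 9.2.2 requires reporting from consent "through 90 days following cessation of study treatment, or 30 days after final dose if the subject initiates new anticancer therapy, whichever occurs first". Section 8.4.3 and footnote w of Table 1.2:1 say the same, and Section 17.5.2 repeats it for the extension part. Under Section 9.2.2, an SAE judged related to treatment or to a protocol-required procedure "should be reported to the Sponsor regardless of the length of time that has passed since study completion".

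The protocol's own analysis text, Section 11.4.3, uses the same 30-day TEAE window but a softer rule: "Statistical analysis and reporting of adverse events will concentrate on treatment-emergent adverse events (TEAEs"). Its incidence sentence names SAEs as an item in their own right: "Incidence of ECIs, SAEs, TEAEs leading to dose modification (reduction/interruption), drug discontinuation or death also be summarized respectively". SAP 15 records changes to the planned analysis as not applicable.

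**The concern.** The analysis window is shorter than the collection window for exactly the events that the protocol chose to follow for longer. Section 7.3.2 gives a reason to expect some of them: "These immune-related AEs (irAEs) may occur shortly after the first dose or several months after the final dose of pembrolizumab". Safety and tolerability, with SAEs named, is a secondary objective.

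A late SAE left out of the tables has no place in the incidence by system organ class, preferred term, severity or relatedness. If it is fatal, it is also missing from the fatal-event table and the fatal-event listing. The death would still count in overall survival, but without an AE term or a causality assessment. In the extension part survival follow-up is discontinued, so even that backstop is weaker. The effect runs one way: reported SAE, related-SAE and fatal-AE incidence for the combination would be too low as a description of what was collected.

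**Working it through.** The plan gives no figure to reproduce. The check compares two windows and then sizes the effect under stated assumptions.

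**Windows after cessation of treatment**

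| Event type | Collected to | Tabulated to (SAP 13.1) | Gap |
|---|---|---|---|
| Non-serious AEs and ECIs | day 30 (Protocol 9.2.1) | day 30 | none |
| SAEs, no new anticancer therapy | day 90 (Protocol 9.2.2) | day 30 | days 31–90 |
| SAEs, new therapy started by day 30 | 30 days after final dose | day 30 | none |
| Related SAEs after day 90 | no time limit (Protocol 9.2.2) | day 30 | all |

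For a subject without new therapy the gap is 90 − 30 = 60 days, which is 60/90 = 67% of the post-treatment SAE period. If new therapy starts between days 31 and 90, the gap depends on how the clause taking the earlier limit is read.

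**Which events fall in the gap**

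1. Onset decides. An event that starts by day 30 and proves fatal later is still a TEAE and stays in the tables.
2. An SAE with onset on days 31–90 is not a TEAE. The general rule and the list heading therefore exclude it from the SAE and related-SAE tables.
3. The fatal-event table is limited to TEAEs by its own title, so it excludes such an event under any reading of the general rule.
4. There is one narrow exception. The missing-date rules in SAP 3.5 set no upper bound, so a late SAE with a missing or partial start date could be classed as a TEAE and tabulated.

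**Size under assumed rates**

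Let p be the proportion of subjects with an SAE starting on days 31–90 without new anticancer therapy. The documents do not give p; 1%, 3% and 10% are assumptions. The values of n are 90, the approximate maximum enrolment across both cohorts (60 + 30), and 30, the Cohort 1 total after stage 2 or the Cohort 2 maximum.

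Expected subjects with an untabulated late SAE = n × p. Probability of at least one = 1 − (1 − p)^n.

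| p | n = 90: expected | n = 90: P(≥1) | n = 30: expected | n = 30: P(≥1) |
|---|---|---|---|---|
| 1% | 90 × 0.01 = 0.9 | 1 − 0.99^90 = 0.595 | 30 × 0.01 = 0.3 | 1 − 0.99^30 = 0.260 |
| 3% | 90 × 0.03 = 2.7 | 1 − 0.97^90 = 0.936 | 30 × 0.03 = 0.9 | 1 − 0.97^30 = 0.599 |
| 10% | 90 × 0.10 = 9.0 | 1 − 0.90^90 = 0.9999 | 30 × 0.10 = 3.0 | 1 − 0.90^30 = 0.958 |

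In a cohort of 30, one subject is 1/30 = 3.3 percentage points of incidence, so a single late event moves the reported rate visibly.

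**The case against.** The strongest reply is that the public text does not settle the matter. The sentence with the general rule is cut by a redaction just after it turns to drug-related events, the table index in SAP 18 is blank, and the list titles say SAEs in some places and TEAEs in others. A separate table of all SAEs cannot be excluded. That limits certainty, and the point is therefore confined to the tables that 13.1 describes. It does not change the natural reading: the list heading and the all-summaries rule govern the SAE tables, and a programmer following the text would drop the late events.

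Second, the SAP can be read as carrying out Protocol 11.4.3 rather than departing from it, and for fatal events the protocol's sentence can itself be read as TEAE-limited. This has force for the fatal table. For SAEs, a restriction is still stricter than a focus, and the protocol's incidence sentence puts no TEAE limit on them. The SAP 15 entry is a secondary matter either way.

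Third, late ascertainment is thinner. The long-term follow-up column of Table 1.2:1 has no mark for AE/SAE assessment, contacts are at least every 3 months, and collection stops early for subjects who start new therapy. That is a good reason not to pool late events with on-treatment ones. It is not a reason to leave them out of the tables, since footnote w and Section 8.4.3 require collection to day 90.

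Finally, the study is exploratory, the SAE listing preserves the data, and the rates used for sizing are assumptions. All true. These points keep this short of a critical defect.

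**Conclusion.** The concern holds. On the natural reading of SAP 13.1, SAEs with onset on days 31–90 in subjects without new anticancer therapy are collected but left out of the SAE, related-SAE and fatal-event tables described there. They remain visible only in the SAE listing, apart from the narrow missing-date exception. The direction is understatement and the size is unknown: under the assumed rates, between 0.9 and 9 of 90 subjects, or 0.3 to 3 of 30.

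The conclusion rests on the visible text of 13.1 and not on the table shells, which cannot be seen, so confidence is medium. The plan should be changed because a secondary safety objective is affected and the remedy is cheap. The primary endpoint, the go/no-go rule and the non-serious AE tables do not depend on it.

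**What to change.** In SAP 13.1, and for consistency in Protocol 11.4.3, state whether the SAE and fatal-event tables are limited to TEAEs. Then:

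- Keep the 30-day window for non-serious AEs.
- Tabulate SAEs, related SAEs and AEs leading to death over the scheduled SAE collection window: 90 days after cessation, or 30 days after the final dose if new anticancer therapy starts. Show onset after day 30 in a separate column or table, so that the thinner follow-up is not mixed with the on-treatment period.
- Widen the listing of fatal events to the same window.
- List related SAEs reported after day 90 and up to database lock separately. Do not add them to the rates, because they are ascertained only if judged related and over an open-ended period.

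The cost is a wording change, one window flag and a few extra table columns. It needs no new visits, because the protocol already requires SAE collection to day 90. Reported SAE counts may rise slightly. Related SAEs that arrive after database lock stay outside the outputs, so the cut-off should be stated.
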